Division: Worldwide Development **Retention Category:** GRS019 **Information Type:** Protocol Amendment

Title:WEUSKOP6416: Evaluating severe events in patients with
Chronic Obstructive Pulmonary Disease (COPD) to inform risk
minimization: A Retrospective Observational Study

Compound Number: CCI18781+GR33343

Effective Date: 26-NOV-2012

Protocol Amendment Number: 01

Subject: COPD, pneumonia requiring hospitalization, Inhaled Corticosteroids (ICS), long-acting bronchodilators (LABD)

Author:

Copyright 2012 the GlaxoSmithKline group of companies. All rights reserved. Unauthorised copying or use of this information is prohibited.

Revision Chronology:

24-JUL-2012	Original	
26-NOV-2012	Amendment No.: [01-	

As specified in the protocol, feasibility was conducted prior to analysis to determine precision of the prespecified study design. The event rate and number of pneumonia events was lower than expected based on feasibility and prior work. As a result, most of the following adjustments were made to the protocol to improve precision regarding estimates of pneumonia.

- The protocol feasibility sections were updated following selection of the new user cohort and development of algorithms to identify episodes of pneumonia and censoring periods.
 Preliminary feasibility had not adjusted for the protocol inclusion/exclusion criteria or analysis requirements.
- The analysis period was expanded from 2005-2010 to 2002-2010 to increase precision to examine pneumonia via identification of additional new users and pneumonia events.
- Severe pneumonia events, hospital-acquired pneumonia (HAP) and severe communityacquired pneumonia (CAP), were combined rather than analyzed separately due to the low number of HAP events.
- The primary endpoints for modeling were clarified to be severe pneumonia events (HAP and severe CAP combined) and all pneumonia events combined rather than HAP, severe CAP and non-

severe CAP separately. These individual endpoints needed to be defined in order to evaluate pneumonia by severity; however, there is more efficiency in combining all events together and then subsetting by severe events than analyzing separately.

- The secondary analysis comparing severe and non-severe CAP was adjusted to include comparisons of patients with pneumonia versus patients without pneumonia on demographics, COPD history, and co-morbid conditions. The original objective was to compare between severe and non-severe pneumonia, however, the small number of events limit the ability to perform multiple logistic regression of severe and nonsevere pneumonia.
- Minor clarification on table shell populations and analyses to improve clarity.

WEUSKOP6416

SPONSOR SIGNATORY:

26 Movember, 2012 Date

SPONSOR INFORMATION PAGE

Study Identifier: WEUSKOP6416

TABLE OF CONTENTS

PAGE

LIS	T OF AB	BREVIA	TIONS	7			
1.	INTRO	DUCTION	١	8			
2.	RATIO	NALE		9			
3.	TARGE	TARGET AUDIENCE9					
4.	OBJEC	TIVES		9			
5.	METHO 5.1. 5.2. 5.3. 5.4. 5.5. 5.6. 5.7.	DDOLOG Feasibilit Study De 5.2.1. 5.2.2. Data Outcome 5.4.1. 5.4.2. 5.4.3. 5.4.3. 5.4.4. 5.4.5. Exposure Confound Analysis 5.7.1. 5.7.2. 5.7.3. 5.7.4. 5.7.5. 5.7.6. 5.7.7. 5.7.8. 5.7.9.	Y y Assessment	10 10 11 11 14 15 16 16 16 16 16 16 22 23 29 29 20 31 33 34 34 34 35			
6.	DISCU	SSION		36			
7.	REFER	ENCES.		37			
8.	TABLE	SHELLS		39			

LIST OF ABBREVIATIONS

AIDS	Acquired Immune Deficiency Syndrome
BMI	Body Mass Index
САР	Community Acquired Pneumonia
COPD	Chronic Obstructive Pulmonary Disease
CPRD	Clinical Practice Research Datalink
EMA	European Medicines Agency
FDA	Food and Drug Administration
FSC	Fluticasone Propionate/Salmeterol Combination
FEV ₁	Forced Expiratory Volume in One Second
FF	Fluticasone Furoate
GOLD	Global Initiative for Chronic Obstructive Lung Disease
CPRD-GOLD	GP OnLine Database
GP	General Practitioner
GSK	GlaxoSmithKline
НАР	Hospital-Acquired Pneumonia
HES	Hospital Episode Statistics
ICS	Inhaled Corticosteroid
ICD	International Classification of Diseases
IPTW	Inverse Probability of Treatment Weighting
LABA	Long Acting Beta Agonist
LAMA	Long-Acting Anti-Muscarinic
LABD	Long-Acting Bronchodilator
MRC	Medical Research Council
OCS	Oral Corticosteroids
PS	Propensity Score
SABA	Short-Acting Beta-Agonist
SAL	Salmeterol
THIN	The Health Improvement Network
QOF	Quality Outcomes Framework
UK	United Kingdom
VI	Vilanterol

Trademark Information

Trademarks of the GlaxoSmithKline group of companies

NONE

Trademarks not owned by the GlaxoSmithKline group of companies

NONE

1. INTRODUCTION

An association has been observed between pneumonia and currently marketed ICScontaining medications relative to non-steroid containing medications among patients with COPD [Ernst, 2007, Crim, 2009; Drummond, 2008; Spencer, 2011; Singh, 2010]. The risk factors for development of pneumonia, including serious pneumonia requiring hospitalization, have been well-characterized in clinical and observational studies and include older age, current smoking, low BMI, certain chronic co morbid conditions (e.g. dementia), higher levels of dyspnoea, and markers of COPD disease severity [Calverley, 2011; Crim, 2009; Mannino, 2009; Müllerova, 2012].

In clinical trials, serious pneumonia was defined as any pneumonia that resulted in death, immediate risk of death (investigator judgment), or hospitalization or prolonged existing hospitalization. In the fluticasone furoate (FF)/vilanterol (VI), an increased incidence of pneumonia, including serious pneumonia was observed with the use of FF/VI compared with VI monotherapy in two one-year-long exacerbation studies (study HZC102970 and study HZC102871). In addition, there were reports of fatal pneumonia in the FF/VI 200/25 treatment group.

In previous studies within the same class of medicines, there was approximately a 1.5 to 2-fold increase in the risk of serious pneumonia, the ICS-containing medication as compared to long-acting beta-agonist (LABA) monotherapy (30 vs. 55 pneumonia episodes per 1,000 person years for 500/50 fluticasone propionate / salmeterol combination [SFC] and 50 salmeterol, respectively [Crim, 2009]. There was no increase in the risk of pneumonia fatality, and results suggested a reduction in mortality in patients taking FSC relative to placebo, but did not achieve statistical significance [Calverley, 2007]. A similar two-fold increase was seen in the two, one-year long studies of FSC vs. SAL studies (data not shown).

In the FF/VI development program, the risk of serious pneumonia was almost three-fold greater for the FF/VI relative to the VI treatment groups (34.9, 37.0, and 33.6 per 1,000 person years for 50/250, 100/25, and 200/25 FF/VI versus 12.1 per 1,000 person years in 25 VI). In addition, inconsistencies in incidence of fatal pneumonia events between the two FF/VI exacerbation studies were noted; however, the low absolute number of fatal events precludes an accurate assessment of the risk or an evaluation of a dose response relationship due to low precision.

2. RATIONALE

Based on the increased risk of serious pneumonia observed in patients randomized to FF/VI, GSK seeks to gain a better understanding of the rates and risk factors for serious pneumonia in patients with COPD using retrospective observational studies of the class of inhaled corticosteroid (ICS)-containing medications.

In addition to quantifying the magnitude of association between ICS and serious pneumonia, this study aims to provide additional information to the previous studies of COPD and pneumonia through examination of risk factors for pneumonia requiring hospitalization (e.g. body mass index [BMI], lung function, current smoking status, dyspnea) not measured in previous observational data sources. Further, it will evaluate statistical interaction between ICS and other risk factors for serious pneumonia. Finally, it will evaluate characteristics of patients with pneumonia who are more likely to be admitted to hospital.

The results will be used to identify patients at greatest risk of pneumonia requiring hospitalization and may identify where risk minimization and/or medical recommendations may be appropriate to prevent pneumonia or improve pneumonia treatment leading to reduced morbidity and mortality.

3. TARGET AUDIENCE

This study will be used by GSK, clinicians, and regulatory agencies to inform on risk factors for pneumonia in patients with COPD for the purposes of risk minimization. The results will be disseminated in a form of manuscripts and scientific presentations. The results are slated to complete in February 2013 to be provided to regulatory agencies. The results will be provided to the Food and Drug Administration (FDA) and the European Medicines Agency (EMA).

4. OBJECTIVES

The overall objectives of this retrospective observational COPD cohort study are:

- to estimate the magnitude of association between risk factors and pneumonia requiring hospitalization, including ICS-containing medications
- to evaluate if ICS-containing medications modify the effect of risk factors for severe pneumonia (i.e. evaluate statistical interaction between ICS × other risk factors)
- among patients with pneumonia, to evaluate any differences in clinical characteristics between patients who have severe pneumonia (requiring hospitalization or contracted in hospital) relative to those with non-severe community acquired pneumonia that did not require hospitalization in the one-year prior following new user Cohort Entry
- to evaluate any differences in clinical characteristics between patients who develop pneumonia or severe pneumonia vs. those who do not develop pneumonia in the one year period following new user Cohort Entry

5. METHODOLOGY

5.1. Feasibility Assessment

Prior to conducting this study, two feasibility assessments were conducted to support the study objectives including a preliminary feasibility assessment and more refined assessment following cohort selection. The feasibility informs on the number of patients in each pre-defined group of new users of respiratory medications and the number of patients meeting different definitions of pneumonia. These figures will allow for an assessment of the available statistical precision to examine treatment group differences.

Mannino and colleagues found a rate of pneumonia requiring hospitalization to be 22.7 per 1,000 person years among patients with advanced disease (GOLD stage airflow limitation III or IV) [Mannino, 2009]. A previous study of community-acquired pneumonia (CAP) in a primary care population of patients with COPD in the GPRD [Müllerova, 2012], there were approximately 40,000 patients with prevalent COPD in CPRD-GOLD between 1996-2006 with ~8% experiencing pneumonia (CAP without restricting to those requiring hospitalization) during the study period with a CAP rate of 22.4 per 1000 person years. The authors included a highly sensitive definition of pneumonia, resulting in 1,469 cases of CAP in their case-control study.

Feasibility results on the 2005-2010 study period included approximately 12,000 new users and 185 pneumonia events. When expanding to include the study period 2002-2010, there will be approximately 18,742 new users of ICS-containing medications (n=12,065) or long-acting bronchodilators (LABD) based on requiring CPRD-GOLD linkage to HES, and hospitalization data 12-mo prior to the new user prescription as presented in Table 1. These totals include the application of all inclusion/exclusion criteria; however, additional subjects may get excluded in the final analysis based on censoring and on-going pneumonia at the time of cohort entry.

Number		F	1	Year o	f Cohort	Entry	F			
of New	0000	0000	0004	0005	0000	0007	0000	0000	0040	T - 4 - 1
Users	2002	2003	2004	2005	2006	2007	2008	2009	2010	lotal
LABD	354	513	703	765	715	723	972	938	994	6,677
ICS-										
containing ^a	1,828	1,499	1,633	1,369	1,310	1,207	1,244	1,100	875	12,065
Total by										
Year	2,182	2,012	2,336	2,134	2,025	1,930	2,216	2,038	1,869	18,742

Table 1 Feasibility Results: New User Cohort

 ICS-Containing=inhaled corticosteroid-containing medications, LABA=long-acting beta-agonists, LAMA=longacting antimuscarinics

5.2. Study Design

This will be a retrospective cohort design.

CPRD-GOLD data will be used to identify a 'new-user' COPD cohort to evaluate a relationship between an exposure to respiratory medications, long-acting bronchodilators (LABD) or ICS-containing medications and the first episode of the pneumonia types of interest.

New users of ICS-containing medications or long-acting bronchodilator (LABD) would be evaluated in a cohort design for the occurrence of pneumonia following their designation as new users. Specific medications are described in Section 5.2.1. To adjust for anticipated differences in confounding by severity between the two treatment groups, important patient characteristics relating to COPD severity and pneumonia would be evaluated in the patient history in the period prior to and including the new user date. Propensity scores (PS) would be generated using these characteristics. The study schematic is presented in Figure 1.

Figure 1 Study Schematic: New User Cohort Design 2002-2010

A strength of the new-user design is that patient follow-up starts with the initial medication prescription written by the healthcare provider for all treatment groups and avoids potential biases that result from examining prevalent users relating to survivor bias and changes in their covariates based on exposure to treatment [Ray, 2003].

5.2.1. New User Study Population

Based on the treatment guidelines, we expect the potential for differences in COPD severity between treatment groups that require adjustment in the analysis. For the treatment of COPD, there is a consensus document on the treatment paradigm for patients with COPD [GOLD, 2009]. A LABD is recommended as an initial maintenance treatment in patients with COPD, including long-acting antimuscarinics (LAMA) or long-acting beta-agonists (LABA). If the disease severity warrants, adding additional therapy (a second bronchodilator or ICS) is recommended. However, an internal unpublished analysis estimated that ~10% of patients at COPD diagnosis are prescribed triple therapy (LABA, LAMA, ICS) during the period 2008 -2009.

CPRD-GOLD data are available through December 22, 2011 with the 1Q2011 data load. HES data are available through August 2011 with the latest data load. Therefore, patients are examined to identify new users between January 2002 and December 31, 2010 to allow for time in the cohort after being identified as a new user and prior to censoring of available data. If the data availability changes, the study period will adjust accordingly in the analysis plan.

The **Baseline Period** is the one-year period prior to Cohort Entry Period to confirm new user status and evaluate patient characteristics of interest.

Identifying New Users

For the purposes of this study, a new user will be defined as someone who has not used medications of interest (ICS-containing or LABD containing medications) in the year prior to a new prescription of a medication of interest (ICS-containing of LABD). The one-year period of no use is referred to a washout period rather than requiring no use of these medications ever in the patient's history. New users of ICS-containing medications and new users of LABD would be identified separately, and are described in Figure 2.

The following patients would not be considered new users:

- New users of triple therapy (LABA/LAMA/ICS) in three single inhalers or ICS/LABA inhaler plus LAMA
- Patients who step up from LABD to ICS/LABA combination therapy in a single device (based on definition of a new user, they have LABD in the history)

ICS New Users. Patients will have at least one prescription for ICS-containing medications from January 2002 (the earliest use) until December, 2010 preceded by a year of no use of ICS-containing medications (ICS monotherapy or ICS/LABA fixed dose combination or ICS/SABA) or LABA or LAMA prior to the new user prescription. At Cohort Entry, Patients who are new users of ICS monotherapy or ICS+LABA or ICS+LAMA in separate inhalers could be included as new users. However, patients prescribed new use of triple therapy (ICS, LAMA, LABA) would be excluded from this analysis.

LABD New Users. Patients will have at least one prescription for LABA or LAMA (but not both) from January 2002 (the earliest use) until December, 2010 preceded by a year of no use of ICS-containing medications (ICS monotherapy or ICS/LABA fixed dose combination or ICS/SABA) or LABA or LAMA prior to the new user prescription.

By definition, patients prescribed new use of triple therapy (ICS, LAMA, LABA) would be excluded from this analysis.

Algorithm to Identify New Users. To identify new users, the following algorithm would be employed. First, patients will be evaluated to see if identify their first prescription of LABD in the analysis period (2002 through 2010). Next patients would be evaluated to see if they are new users of ICS-containing medications in a similar manner. Patients

will be included in the analysis only once. As patients could conceivably qualify as new users more than once during the study period or be on more than one medication during the study period, the first prescription defining a patient as eligible for the study (either as new user of LABD or new user of ICS) during the study period only would be evaluated. As patients generally tend to fill multiple prescriptions for COPD in a year and add therapies rather than switch therapies in COPD, subsequent prescriptions would not be evaluated for new use moving forward to the end of available data, as this is expected to yield few patients. In the case of data anomalies where a patient is prescribed ICS/LABA fixed dose combination with either LABA or ICS monotherapy, the patient will be considered as having an ICS/LABA new user prescription.

The date when patients become new users of LABD or ICS-containing medications is considered the **Cohort Entry Date**.

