5.2.2. Inclusion / Exclusion Criteria

Inclusion Criteria

Patients are required to:

- 1. Have CPRD-GOLD data of acceptable research quality according to CPRD standards.
- 2. Be new users of LABD or ICS-containing medications from January 2002-December 2010
- 3. Have a COPD diagnosis at any time in the period prior to and including the Cohort Entry Date (to eliminate any patients with asthma only)
- 4. Have at least one year of data prior to Cohort Entry Date.
- 5. Be at least 45 years of age at Cohort Entry Date.
- 6. Have GPRD-HES linkage. (Note: these individuals need to be retained for basic demographics but are not part of the new user cohort).
- 7. Have HES coverage one year prior to the Cohort Entry Date

Exclusion Criteria

1. Patients with an occurrence of a code for a medical condition incompatible with COPD diagnosis any time in their history. This list contains conditions that are a related to lung or bronchial developmental anomalies, degenerative processes (cystic fibrosis, pulmonary fibrosis), bronchiectasis, pulmonary resection or other significant respiratory disorders other than COPD (but not including cancer) that can interfere with clinical COPD diagnosis or substantially change the natural history of the disease.

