5.5. Exposure

The primary exposure of interest is ICS, evaluated in new user cohort of ICS-containing medications. The comparator exposure group of interest is LABD.

To account for poor adherence to respiratory medications, patients will be classified as exposed to study medication for the duration of prescribed therapy plus 30 days. When the duration of prescribed therapy cannot be determined due to missing information, it will be assumed to be a 30-day supply to correspond to the amount of medications in a single inhaler. In the case of a single inhaler, patients will allow for gaps of up to 90 days between prescriptions.

To identify a study population of long-term users, we will conduct a secondary analyses restricted to patients on treatment for greater than 6 months. The long-term users would allow for examination of cumulative doses. Gaps between each dispensing of up to 90 days will be allowed. A patient dispensed a single inhaler on the Cohort Entry Date would be censored at 90 days if they did not have another prescription. A patient dispensed a single inhaler on day 40 would experience 99 days of coverage (i.e., 39 days of coverage for the first inhaler and 90 days for the second inhaler).

The strength of the new user prescribed ICS medication on the Cohort Entry Date will be categorized into equipotent doses of low, medium, and high-dose ICS based on classification according to Figure 3-1 presented in the Global Initiative for Asthma (GINA) guidelines [GINA, 2011]. The strength of the new user prescription would be entered into the Cox model primary outcome models as low, medium, and high relative to LABD (e.g. dummy variables). The strength of the medication will be tabulated based on the prescription on the Cohort Entry Date.

The use of other medications during the one-year **Baseline Period** will be included in the model as a marker of disease severity.

Prescriptions (Yes/No) during the Baseline Period indicative of disease severity. In addition, the number of prescriptions (except oxygen use) for the following will be collected:

- short-acting bronchodilators (short-acting anticholinergics or short-acting betaagonists, including combination inhalers)
- long-term oral corticosteroid use (>4 Rx in 12 months)
- theophyllines

- oxygen use. when recorded (changes in reimbursement censor this information during part of the analysis period, but we will capture what information is available)

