5.6. Confounders

Key risk factors for pneumonia that may also relate to treatment will be measured in the one-year Baseline Period. For the purposes of general co-morbidity assessment and vaccination for pneumonia, a longer history will be examined. Although patients may have varying periods of history, this is not expected to be differentially recorded by treatment (which could result in information bias). A longer look back period is needed to identify co-morbidities given they may not be recorded in the Baseline Period.

Confounders that are based on "counts" of healthcare encounters and exacerbation will be categorized during analysis (e.g., tabular summaries, propensity score creation, Cox modeling).

Variable	Parameterization
Age at Cohort Entry	Age will be treated either as a continuous variable, or as a categorical one (see Table shells for intervals)
Gender	Male=1 or Female=0
Body Mass Index (BMI) during Ever in Patient History	Weight in kilograms divided by height in meters squared, will be utilised as a categorical variable using the following categories widely referenced as WHO classification: Underweight (Below 18.5), Normal (18.5 - 24.9), Overweight (25.0 - 29.9), and Obese (30.0 and greater).
	For modelling, the following cutoff values will also be examined: BMI<21, BMI 21-24.9, BMI ≥25.
Smoking status during Ever in Patient History	Four categories will be created: ex-smoker, current smoker, non-smoker, and unknown smoking status containing patients with missing entries or other types of tobacco exposure (e.g. passive smoking). Non-smoker will be the referent group in modelling.
Overall Social Deprivation Scores for England	The deprivation quintile is derived the 32,482 areas of social deprivation, with 1 being most deprived and 32,482 being least deprived. quintiles will be identified as follows (with least deprived the referent in modelling). Quintiles are provided by CPRD:

Variable	Parameterization
Townsend Scores	Quintile. Townsend scores will be described by quintile, as provided by CPRD-GOLD.
Charlson Co-morbidity index and individual chapters Ever in Patient History (prior to Cohort Entry Date)	Charlson's comorbidity index chapter indicator measures will be created using a recently published algorithm by Khan and colleagues [Khan, 2010] after removing COPD and AIDS from the disease list. Some patients may have COPD and some may not (incident diagnosis). AIDS will be excluded due to very low prevalence in the general population.

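### ICS or LABD use before the one-year washout is not in the propensity score, which leaves a possible residual confounder that is cheap to check

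*Protocol*

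**What the plan says.** Protocol Section 5.2.1 states openly that the year without use is a "washout period rather than requiring no use of these medications ever in the" patient's history. The same rule serves both groups: entry must be "preceded by a year of no use of ICS-containing medications (ICS monotherapy or ICS/LABA fixed dose combination or ICS/SABA) or LABA or LAMA". Section 5.2.2 sets the minimum record length: "Have at least one year of data prior to Cohort Entry Date".

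Section 5.2 names as a strength of the new-user design that "patient follow-up starts with the initial medication prescription written by the healthcare provider for all treatment groups", and says this avoids survivor bias and covariates altered by treatment. Section 5.7.2 gives the operative rule, which starts follow-up at the first eligible prescription.

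Section 5.7.4 fills the propensity model with the variables of Sections 5.5 and 5.6. In Section 5.5, use of other medications in the one-year Baseline Period "will be included in the model as a marker of disease severity". The list covers short-acting bronchodilators, "long-term oral corticosteroid use (>4 Rx in 12 months"), theophyllines, oxygen, nebulized therapy and roflumilast. Section 5.6 looks further back for some items: "For the purposes of general co-morbidity assessment and vaccination for pneumonia, a longer history will be examined". BMI and smoking are also read from the whole history. Past ICS, LABA or LAMA use is in neither section, nor in the shells of Tables 7, 8 and 11, and Section 6 does not name it as a limitation.

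**The concern.** Someone who stopped ICS and restarts 13 months later enters as an ICS new user. Someone who stopped ICS two years ago and now receives a LABD enters as a LABD new user. In the Baseline Period both have no ICS or LABD use by definition, so no listed medication variable separates them directly from a first-time user.

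Past use could plausibly relate to the class prescribed now, and to pneumonia risk through tolerance of earlier treatment, stopping after harm, or longer-standing disease. These routes are my reasoning; the protocol does not state them. They pull in different directions. What is at stake is the primary ICS versus LABD hazard ratio, which Section 5.7.8 hopes will exclude margins of 2.0 for severe pneumonia and 1.5 for all pneumonia.

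**Working it through.** **The plan's own figures.** Section 5.7.8 uses about 12,000 ICS and 6,600 LABD users.

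- Severe pneumonia, 4 against 7.4 per 1,000 person-years: 6,600 × 0.004 + 12,000 × 0.0074 = 26.4 + 88.8 = 115.2 events (stated 115). A two-sided two-proportion test at 0.05 gives 82.8% power (stated 82%).
- All CAP, 11 against 16.4 per 1,000 person-years: 72.6 + 196.8 = 269.4 events (stated 270), with power 85.2% (stated 85%).

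These figures reproduce, and nothing here changes them.

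**Can past users enter?** Yes. Section 5.2.1 asks for one free year and Section 5.2.2 for one year of record. I take that washout as operative. A sentence in Section 5.7.1 reads as if ICS new users might have had ICS in the year before entry; it conflicts with Section 5.2.1 and should be reconciled separately.

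**Is past use adjusted for?** Not directly. The respiratory drugs in Section 5.5 are confined to the Baseline Period. The longer look-backs in Section 5.6 cover co-morbidity (including asthma ever), pneumococcal vaccination, BMI and smoking.

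**How large could the effect be?** The protocol gives neither the share of returning users in each group (p) nor their pneumonia rate relative to first-time users (RR). All inputs below are therefore assumptions. With no other adjustment, the hazard ratio is multiplied by about

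B = [1 + p_ICS × (RR − 1)] / [1 + p_LABD × (RR − 1)].

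Example: p_ICS = 0.40, p_LABD = 0.10, RR = 1.5 gives B = 1.20 / 1.05 = 1.143.

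| Assumed share, ICS / LABD | RR 0.7 | RR 1.5 | RR 2.0 |
|---|---|---|---|
| 10% / 10% | 1.000 | 1.000 | 1.000 |
| 20% / 10% | 0.969 | 1.048 | 1.091 |
| 40% / 10% | 0.907 | 1.143 | 1.273 |
| 10% / 20% | 1.032 | 0.955 | 0.917 |

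For scale, the unweighted standard error of the log rate ratio at the planned severe-pneumonia counts is √(1/26.4 + 1/88.8) = 0.222. A factor of 1.048 shifts the log hazard ratio by 0.047, about 0.2 of that; a factor of 1.143 shifts it by 0.134, about 0.6. For all pneumonia the standard error is √(1/72.6 + 1/196.8) = 0.137, and 0.134 is about one standard error.

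**The case against.** The strongest reply is that the washout is a disclosed design choice applied alike to both groups. A mixed ICS group is compared with a mixed LABD group, and with equal shares B is 1. A reader might infer that returning users are set against first-time users with no adjustment. The documents do not support that: they show no imbalance, and the propensity score holds asthma ever, GOLD stage, exacerbation counts, prior pneumonia, baseline respiratory therapy, GP visits, hospitalizations and year of entry. These take up part of what accompanies past use, so B overstates what would remain to the extent that they do.

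The entry algorithm in Section 5.2.1 also limits the number of returners. Each patient enters once, at the first eligible prescription in 2002–2010. Returners are therefore mainly people whose earlier use came before 2002, before their record began, or before they met the other criteria.

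The Section 5.2 sentence is mainly loose wording, since Section 5.7.2 states the real start and Section 6 claims only that bias is minimized. The protocol also expects a statistical analysis plan to refine the modelling.

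Most of this stands and it lowers the weight of the point. It does not remove it. Section 5.7.4 itself says where the propensity variables come from, and past use of the study drugs is not there. The protocol already accepts a longer, unequal look-back for co-morbidity because one year may miss it; the same reasoning applies to earlier exposure.

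**Conclusion.** The gap is real but conditional. Earlier ICS or LABD use is permitted by design and is not a propensity-score variable. It biases the hazard ratio only if two things hold: the share of returning users differs by group, and past use relates to pneumonia risk beyond the listed covariates. The protocol is silent on both, so direction and size are unknown.

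A reader might take a factor such as 1.143 as an estimate of the bias. It is not: it rests on assumed shares of 40% and 10% and an assumed rate ratio of 1.5, and reversing the order of the shares reverses the direction. Nor do the documents show that the new-user design fails. This is an inexpensive improvement that should be made, together with a wording correction, and not a demonstrated error in the primary analysis.

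**What to change.** - Add to Section 5.6 and to the propensity model two indicators, any recorded ICS use and any recorded LABD use before the washout year, together with years of available history.
- Tabulate all three by treatment group alongside Tables 7 and 8. This alone shows whether an imbalance exists.
- Repeat the primary severe-pneumonia model in patients with no recorded earlier ICS or LABD use, ideally among those with a longer minimum history.
- In Section 5.2, describe the start of follow-up as the first eligible prescription after a one-year washout, in line with Section 5.7.2.

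The cost is three covariates from records already held, one table addition and one extra model run. There are three downsides. Earlier use is visible only where the record exceeds one year, so short-history patients may be misclassified as never users; the years-of-history term and the longer minimum history help only in part. The restricted rerun will have fewer events than the 106 severe CAP and 1 HAP in Table 4, so it should be read as a check on the estimate, not as a test. A strong predictor of treatment may also widen the weights somewhat and bring more patients over the threshold of 10 that Section 5.7.4 sets for review.
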